1.8.2 Secondary

- 1.8.2.1 Patients achieving pCR based on neoadjuvant treatment with a combination of binimetinib and encorafenib will demonstrate a greater decrease in FLT-PET uptake (from baseline to 8 weeks post neoadjuvant treatment initiation) compared to non-pCR patients.
- 1.8.2.2 Lower post-therapy FLT-PET SUVmax is associated with higher likelihood of pCR.
- 1.8.2.3 Change in FLT-PET uptake will correlate with Ki-67 changes in tumor cells. In particular, the change in FLT-PET uptake (from baseline to 8 weeks post neoadjuvant treatment initiation) will directly correlate with the change in early (from baseline to 2 weeks) and post therapy (from baseline to 8 weeks after neoadjuvant treatment initiation) specimen Ki-67 assays.
- 1.8.2.4 Immune effects of treatment with BRAFi + MEKi. CD8+ T cell infiltration at baseline, and/or the change in CD8+ tumor infiltrating lymphocytes (TIL) with treatment early (on treatment biopsy) and late (at resection), in the tumor or tumor bed directly correlates with pCR, disease free survival (DFS) and overall survival (OS).

2. Objectives

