9.7.3.1 Primary imaging aim

To compare the change in ^{18}F -FLT PET/CT uptake (from baseline to post-neoadjuvant therapy) among patients with and without pathologic complete response.

The primary imaging aim consists of evaluating whether the anticipated decrease in ^{18}F -FLT PET/CT uptake from the baseline scan to the post-neoadjuvant scan will be greater in pCR versus non-pCR subsets, among patients with clinically resectable or radiographically-detected stage IIIB/C/D melanoma being treated with the neoadjuvant combination of encorafenib (a selective BRAF inhibitor) and binimatinib (a MEK inhibitor).

Distributional summaries of the continuous percent change in ^{18}F -FLT PET/CT SUVmax will be reported, where percent change is defined as $(\text{baseline SUVmax} - \text{post-neoadjuvant SUVmax}) / (\text{baseline SUVmax}) * 100\%$. The comparison of percent change in SUVmax between pCR and non-pCR patients will be performed using a one-sided nonparametric Wilcoxon rank sum test with an alpha level of 0.05.

Of the 42 accrued patients, we assume that 34 (81%) will have interpretable ^{18}F -FLT PET/CT scans at both time points. The mean percentage decrease in SUVmax for non-pCR versus pCR is assumed to be 30% and 50%, respectively, and the standard deviation is assumed to be 20% for both groups. Given that melanoma is expected, on average, to be more proliferative than the breast cancers studied in ACRIN 6688, positing an expected 20% difference in mean percentage decrease in uptake seems justified (55). With a pCR rate of 57%, a sample size of 34 analyzable cases will yield 86% power with a one-sided type I error rate of 0.05 based on the Mann-Whitney Wilcoxon test using Monte Carlo simulation ($n=100,000$) from appropriate null and alternative normal distributions (PASS 2019); however, the power of this comparison varies depending on the pCR rate. For example, it is 84% with a pCR rate as low as 35%, and 83% with a pCR rate as high as 65%.

For the sake of completeness, we will also report distributional summaries and comparisons for percent change in ^{18}F -FLT PET/CT SUVpeak; however, the prespecified primary comparison will be based on ^{18}F -FLT PET/CT SUVmax.

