9.7.3.2 Secondary imaging aims

Secondary imaging aim #1: To compare post-neoadjuvant ^{18}F -FLT PET/CT uptake among patients with and without pathologic complete response.

This secondary imaging aim will be analyzed in a similar manner to the primary imaging aim, but using post-neoadjuvant ^{18}F -FLT PET/CT SUVmax, as opposed to percent change ^{18}F -FLT PET/CT SUVmax.

Again, for completeness, we will also report distributional summaries and comparisons for post-neoadjuvant ^{18}F -FLT PET/CT SUVpeak.

Secondary imaging aim #2: To estimate an optimal threshold for prediction of pathologic complete response using i. change in ^{18}F -FLT PET/CT uptake, and ii. post-neoadjuvant ^{18}F -FLT PET/CT uptake.

This secondary imaging aim consists of evaluating the diagnostic performance of ^{18}F -FLT PET/CT uptake as a marker of pathologic complete response (pCR), and of estimating the optimal threshold (binary cutpoint) and associated sensitivity/specificity.

Diagnostic performance of percent change in ^{18}F -FLT PET/CT SUVmax (from the baseline scan to the post-neoadjuvant scan) as a marker for pCR status will be assessed using receiver operating characteristic curve (ROC) analysis. In particular, the empirical area under the receiver operating characteristic curve (ROC AUC) will be reported, along with corresponding 95% confidence interval. In addition, we will formally test if the ROC AUC exceeds 0.5 using a one-sided test as suggested by DeLong et al (56) with an alpha level of 0.05. Finally, the optimal threshold (binary cutpoint) of continuous percent change in SUVmax will be estimated by means of the Youden index (57). In order to properly reflect sampling variability, a 95% confidence interval for the optimal threshold will be estimated using the bootstrap technique (58).

The corresponding performance of the optimal threshold (measured via sensitivity and specificity) will be estimated using cross-validation. In particular, we will randomly divide the cohort into 5 folds. Using 4 folds, the ROC curve will be fit and optimal threshold (Youden index) obtained. This threshold derived from the 4 folds will then be applied to the subjects in the remaining holdout fold, in order to

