define each holdout subject as test positive ($>$ threshold) vs. test negative (\leq threshold). This step will be repeated until every subject has been a holdout and has test result (positive/negative) defined. Sensitivity and specificity will then be calculated and reported, using the test result for each subject defined during holdout.

The proposed sample size of 42 patients (34 analyzable), assuming a pCR rate of 57%, yields a minimum of 81% power to reject the null hypothesis of an uninformative marker (ROC AUC=0.5) based on a one-sided test with type I error rate of 0.05, assuming the true ROC AUC is 0.74 or higher (PASS 2019).

In addition, estimates of diagnostic performance will be reported for percent change in ^{18}F -FLT PET/CT SUVpeak.

This analysis will be repeated separately for post-neoadjuvant ^{18}F -FLT PET/CT uptake.

Secondary imaging aim #3: To assess the correlation between change in ^{18}F -FLT PET/CT uptake and change in Ki-67.

This secondary imaging aim consists of assessing the correlation between the anticipated decrease in ^{18}F -FLT PET/CT (from the baseline scan to the post-neoadjuvant scan) and the change in tumor cell Ki-67 (from baseline to post-neoadjuvant therapy).

The correlation between percent change in continuous SUVmax and percent change in the continuous Ki67 score will be estimated using the Spearman correlation coefficient. A one-sided correlation test with null hypothesis of zero correlation will be conducted at alpha level of 0.05. The corresponding confidence interval for the estimated Spearman correlation coefficient will also be reported.

The proposed sample size of 42 patients (34 analyzable) yields a minimum of 83% power to detect a nonzero correlation, assuming that the true correlation is 0.5 or higher. A two-sided Spearman correlation test with a type I error rate of 0.05 was used for this computation based Monte Carlo simulation ($n=100,000$) from a bivariate normal distribution (PASS 2019).

Correlation between change in ^{18}F -FLT PET/CT and the early change in tumor cell Ki-67 (from baseline to the week 2 interim biopsy) will also be separately estimated; however, as the week 2 interim biopsy is not mandatory, we expect small numbers of subjects, and thus this analysis will be exploratory. The corresponding correlation with percent change in ^{18}F -FLT PET/CT SUVpeak will also be reported.

10. Specimen Submissions

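### Section 9.7.3.2, imaging aim #2: the ROC rules are written for percent decrease in SUVmax and repeated for post-treatment uptake without reversing direction, although hypothesis 1.8.2.2 expects low uptake in pCR

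*Combined protocol and SAP*

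**What the plan says.** Section 9.7.3.1 defines percent change as baseline minus post-treatment SUVmax, divided by baseline, so a larger value is a larger fall. The planning assumption follows that orientation: "The mean percentage decrease in SUVmax for non-pCR versus pCR is assumed to be 30% and 50%, respectively".

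Aim #2 in Section 9.7.3.2 covers two markers: (i) change in uptake and (ii) post-neoadjuvant uptake. The method is written out for the first only. On the AUC it says "we will formally test if the ROC AUC exceeds 0.5 using a one-sided test". In the 5-fold cross-validation, the threshold from four folds is used to "define each holdout subject as test positive" if the value lies above it and negative otherwise. The second marker is handled by one sentence: "This analysis will be repeated separately for post-neoadjuvant" uptake.

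Hypothesis 1.8.2.2 gives the expected direction for that second marker: "Lower post-therapy FLT-PET SUVmax is associated with higher likelihood of pCR".

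Aim #1 in the same section compares post-treatment uptake between pCR and non-pCR patients. It refers back to the one-sided Wilcoxon test of the primary imaging aim and does not state which side.

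**The concern.** For percent decrease, testing for an AUC above 0.5 and calling high values positive are both right. For post-treatment uptake, the protocol's own hypothesis puts the pCR patients at the low end. With high values still treated as indicating pCR, the expected AUC is below 0.5, the one-sided test looks in the wrong tail, and the Youden search looks for a cut-point on the wrong side.

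Part ii exists to deliver a threshold with its sensitivity and specificity, and these are the outputs that a literal repeat would spoil. The planned bootstrap interval would then surround the same misdirected threshold.

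**Working it through.** **Inputs.** From Section 9.7.3.2: 34 analysable patients, pCR rate 57%, one-sided alpha 0.05, true AUC 0.74, stated power 81%. Since 0.57 × 34 = 19.4, take n1 = 19 pCR and n0 = 15 non-pCR. The documents give no effect size for post-treatment SUVmax. The mirror image of the planned AUC, 1 − 0.74 = 0.26 in the written orientation, is therefore an assumption.

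**Step 1: reproduce the plan's figure.** Hanley-McNeil variance:

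Var(A) = [A(1−A) + (n1−1)(Q1−A²) + (n0−1)(Q2−A²)] / (n1·n0), with Q1 = A/(2−A) and Q2 = 2A²/(1+A).

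- A = 0.50: Q1 = Q2 = 0.3333. Var = (0.25 + 18 × 0.0833 + 14 × 0.0833)/285 = 0.01023, SE = 0.1012.
- A = 0.74: Q1 = 0.5873, Q2 = 0.6294. Var = (0.1924 + 18 × 0.0397 + 14 × 0.0818)/285 = 0.00720, SE = 0.0849.
- Power = Φ[(0.74 − 0.50 − 1.645 × 0.1012)/0.0849] = Φ(0.867) = 80.7%.

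The Obuchowski approximation gives 81.4%. A simulation of the DeLong test (20,000 binormal data sets) gives 82.3%. The stated 81% is reproduced.

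**Step 2: literal repeat for post-treatment uptake.**

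- A = 0.26: Q1 = 0.1494, Q2 = 0.1073. Var = (0.1924 + 18 × 0.0818 + 14 × 0.0397)/285 = 0.00779, SE = 0.0883.
- Power = Φ[(0.26 − 0.50 − 1.645 × 0.1012)/0.0883] = Φ(−4.60) = 0.000002.

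The DeLong simulation gives 0.00005, which is zero for practical purposes. This does not hang on 0.26: a one-sided test for AUC above 0.5 rejects less often than its null rate whenever the true AUC is below 0.5.

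**Step 3: direction reversed.** With low uptake scored as indicating pCR, the same data have AUC 0.74. Power is 80.7% by formula and 82.0% by simulation.

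**Step 4: cut-point performance.** Simulated 5-fold Youden cross-validation, 19 v 15, same assumed effect, with J = sensitivity + specificity − 1 (ranges are over repeated simulations):

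| Rule | Sensitivity | Specificity | J at central values |
|---|---|---|---|
| Literal (positive above threshold) | 0.75–0.76 | 0.16–0.18 | 0.76 + 0.17 − 1 = −0.07 |
| Reversed (positive at or below threshold) | 0.66–0.68 | 0.63–0.65 | 0.67 + 0.64 − 1 = 0.31 |

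The literal rule keeps a respectable sensitivity only by calling most patients positive. J near zero means that it does not discriminate.

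**Step 5: what a literal analysis would still show.** Aim #2 also reports the empirical AUC with a 95% interval. With the Step 2 standard error, an estimate of 0.26 has an approximate interval of 0.26 ± 1.96 × 0.0883, or 0.09 to 0.43, wholly below 0.5.

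**The case against.** The strongest reply is that the rules are carried over by reference and never restated for post-treatment uptake. Nowhere does the plan say that high post-treatment uptake is positive. Hypothesis 1.8.2.2 fixes the intended direction in advance, and orienting a ROC curve by the hypothesis is routine, so a competent analyst would probably do it. This stands as to intent. It does not remove the gap, because the analyst would have to depart from an explicit rule that the plan says to repeat. Nor is leaving orientation to be settled at analysis harmless. In the null simulation the DeLong test rejected in 5.5% of runs upward and 5.6% downward, so choosing the direction from the data would give about 11% error in place of 5%.

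Two stronger readings are tempting, and the documents support neither:

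- **That the plan cannot detect the effect at all.** The AUC interval (Step 5) and the planned distributional summaries of post-treatment uptake by pCR status would show the inverse association. Only the formal test and the cut-point results fail, and only on a literal reading.
- **That aim #1 contains the same error.** Aim #1 carries over a one-sided Wilcoxon test by loose analogy. It has no above-threshold or AUC-above-0.5 rule that could point the wrong way, and hypothesis 1.8.2.2 supplies the direction. Its direction is unstated locally, which is not the same as wrong.

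It is also fair to say that near-zero power is what any one-sided test gives in the wrong tail, and that the 0.26 is assumed.

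**Conclusion.** The point holds for part ii of imaging aim #2. The written rules, repeated as instructed, run against the protocol's own hypothesis for post-treatment uptake, and no other section reverses them.

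The qualitative conclusion needs only the direction in 1.8.2.2. The figures of about 0% v 82% power, and of J about −0.07 v 0.31, also rest on three assumptions: the mirror-image AUC, a 19/15 split, and binormal data with equal variances.

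The reach is limited to one part of a secondary imaging aim. The pCR endpoint and two-stage design, the primary imaging aim, the percent-change ROC analysis and the 81% power figure all stand. It is worth correcting before the imaging data are analysed.

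**What to change.** Add to aim #2 in Section 9.7.3.2:

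> For post-neoadjuvant SUVmax and SUVpeak, lower values indicate pCR: test positive is at or below the threshold, AUC is P(uptake in non-pCR > uptake in pCR), and the one-sided alternative is AUC > 0.5 in that orientation.

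As a clarification only, state in aim #1 that the one-sided alternative is lower post-treatment uptake in pCR patients.

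The cost is one or two sentences. No patients, scans or sample-size changes are needed.

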10.1 Submissions to ECOG-ACRIN Central Biorepository and Pathology Facility (CBPF)

The submission of baseline diagnostic and surgical tumor tissue is required for central diagnostic review and pathologic response assessment. Additional tumor tissue from these procedures and from biopsies performed for research from patients who agree to participate in the laboratory research studies are also requested. Tumor tissue is to be submitted within one month of registration or collection.

The tumor tissue specimens are to be labeled with the institution's assigned pathology ID# as well as the information above. If only slides are submitted, slides are to be adequately labeled and numbered in the order sectioned from the block.

Submitting pathologist and clinical research associate may refer to [Appendix I](#) which outlines the Pathology Submission Guidelines.

10.1.1 Form Submission Requirements

The following **forms** must be submitted with all pathology submissions.

- STS generated shipping manifest form
- Copy of the institutional diagnostic and surgical pathology reports
- Immunological study reports, if available

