2.3 Correlative Science Objectives

2.3.1 To evaluate CD8+ T cell infiltration and Ki-67 status in tumor or tumor bed pre, during, and post neoadjuvant treatment and the change in CD8+ TIL with neoadjuvant treatment and correlate with clinical response.

2.3.2 To compare local review for pathologic response with central pathology review.

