7.2 Biological Sample Submissions

1. Specimens are to be submitted as outlined in Section [10](#).
2. All specimens submitted must be entered and tracked via the online ECOG-ACRIN Sample Tracking System (STS).

Biological Materials	Baseline	After Two [2] Weeks of Treatment ⁴	After Eight [8] Weeks of Treatment	Week 20 ⁶	Week 32 ⁶	Week 44 ⁶	End of Treatment
Mandatory for Central Diagnostic Review							
FFPE Tumor Tissue ⁷	X ¹		X ⁵				
Collect and submit from patients who answer “Yes” to “ I agree to have one or two research biopsies to collect tissue for known laboratory research studies. ”							
Tumor Tissue Biopsy ⁷	X ³	X					
Collect and submit from patients who answer “Yes” to “ I agree to have my tissue samples collected from procedures performed as part of my standard of care and I agree that my tissue samples and related health information may be used for the laboratory research studies described above. ” ⁸							
FFPE Tumor Tissue	X ¹		X ⁵				
Collect and submit from patients who answer “Yes” to “ I agree to provide additional blood samples for future health research. ” ⁸							
Peripheral Blood (ten 10mL green top heparin tubes) ²	X	X	X	X	X	X	X
Peripheral Blood (two 10mL SST red top tubes) ²	X	X	X	X	X	X	X
Peripheral Blood (one 10mL Streck Cell-Free DNA tube) ²	X	X	X	X	X	X	X

1 Tumor tissue collected within two (2) months prior to performance of imaging and from the surgical resection with the related pathology reports must be submitted for central diagnostic review within one (1) month following registration and the procedure respectively. Failure to submit the required materials may render the case unevaluable. Additional materials are requested for laboratory research studies from patients who consent “Yes” to “*I agree to have my tissue samples collected from procedures performed as part of my standard of care and I agree that my tissue samples and related health information may be used for the laboratory research studies described above.*”

- 2 Kits are being provided for the collection and shipment of the peripheral blood specimens. See [Appendix VII](#) for instructions. Kit orders will on average be delivered within three (3) business days from the time the order is placed.
- 3 If baseline biopsy is performed after study registration, the baseline FLT-PET/ CT scan should be completed prior to biopsy (can be done same day).
- 4 +/- 1 week.
- 5 Surgical resection specimen.

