9.2 Study Endpoints

Of the 42 patients accrued, we expect at least 39 patients will be evaluable. The main analysis for clinical endpoints will be based on 39 evaluable patients. Based on prior studies, it is not expected that there will be significant issues with disease progression or severe toxicities that interfere with planned surgical resection.

A pCR will be defined as the absence of residual viable melanoma in the resected metastasis site as assessed on local pathology review.

Overall Survival (OS) will be defined as the time from enrollment to death from any cause. Patients who have not died will be censored at the date last known to be alive. Disease-Free Survival (DFS) will be defined as the time from complete surgical resection to disease progression or death (whichever occurs first). Patients who are not eligible for resection will not be included in this analysis. Cases who have not had an event will be censored at the date of last disease assessment documenting the patient was free of progression. Progression will be evaluated based on international criteria proposed by the revised Response Evaluation Criteria in Solid Tumors (RECIST) guideline (version 1.1) as described in Section [6](#). Response will be defined by the RECIST guidelines (version 1.1) as described in Section [6](#). Toxicity will be defined using the CTCAE.

Ki-67 IHC in tumor cells will be graded as a percentage of total number of tumor cells with nuclear staining (to the nearest 10%) over 10 high powered fields (at 20X magnification).

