Representative tumor tissue from the involved lymph node (not a primary melanoma) (block preferred) and related pathology reports from a procedure performed within two (2) months prior to the performance of imaging and from the surgical resection after eight (8) weeks of treatment must be submitted for central diagnostic review. Additional tumor tissue and peripheral blood specimens are to be collected and submitted per patient consent.

- Additional tumor tissue from the archived pre-trial biopsy and surgical biopsy
- Tumor tissue from research biopsies performed prior to start of treatment, if performed, and after two (2) weeks (+/- 1 week) off treatment
- Peripheral blood specimens for potential future research studies

All specimens must be clearly labeled with the ECOG-ACRIN protocol number [EA6183], the patient's initials and ECOG-ACRIN patient sequence number, the collection date, and specimen type. For pathology materials, it is strongly recommended that full patient names be provided.

It is required that all specimens submitted on this trial be entered and tracked via the ECOG-ACRIN Sample Tracking System (STS) (Section [10.4](#)). An STS shipping manifest form is to be included with every submission.

If you have any questions concerning tumor tissue and peripheral blood submissions or need information regarding potential alternative submission requirements, please contact the ECOG-ACRIN CBPF at [contact] or [contact].

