10.3 Central Laboratory: Processing and Routing

Pathology materials will be distributed to investigators for central pathology review and defined laboratory research studies described in Section [11](#).

Specimens submitted will be processed to maximize their utility for current and future research projects and may include, but not limited to, extraction of plasma, serum, DNA and RNA.

Specimens from patients who consented to allow their specimens to be used for future approved research studies, including residuals from the currently defined research studies, will be retained in an ECOG-ACRIN designated central repository. For this trial, specimens will be retained at the ECOG-ACRIN Central Biorepository and Pathology Facility. Specimens will be de-identified prior to distribution for any approved research projects.

If future use is denied or withdrawn by the patient, the specimens will be removed from consideration for use in any future study. Pathology materials may be retained for documentation purposes or returned to the site. All other specimens will be destroyed per guidelines of the respective repository.

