11.1 Central Diagnostic Review

The baseline diagnostic and surgical resection tumor tissue is required for central diagnostic review to determine patient evaluable for the trial and for central pathologic response assessments.

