NOTE: A three-dimensional macroscopic measurement of the largest grossly positive identified lymph node should be provided in the gross description accompanying the specimen. If the largest grossly positive lymph node measures < 5 cm in greatest dimension, then each grossly positive lymph node should be submitted entirely at 2 mm serially sectioned intervals. For any grossly positive lymph node measuring > 5 cm in greatest dimension, representative sections of the largest lymph nodes may be utilized to avoid oversampling. Following serial sectioning of each lymph node, for those nodes > 5 cm, sections representing a complete cross section of the entire surface area should be submitted per 1 cm of each grossly positive lymph node. Sections submitted should include grossly obvious tumor. All grossly positive lymph nodes < 5 cm in specimens (where the largest node(s) exceeds 5 cm) should be submitted entirely.

From Consenting Patients:

Research Biopsies

- Representative formalin-fixed paraffin-embedded (FFPE) tumor tissue blocks from baseline following step 1 registration (prior to treatment) and two weeks post treatment biopsy.

NOTE: This baseline research biopsy is requested only if there is no material available from a prior procedure performed within two (2) months of imaging.

Biopsies to obtain specimens for research must be determined to be minimal risk prior to performance. Tumor tissue specimens are to be obtained from the target lymph node metastases, with or without image guidance. Types of biopsies are to include: 3-4 (1-2 cm in length), 14-16 or 18-gauge core biopsies, or small incisional biopsies (tumor biopsy at least 4-5 mm in diameter) such that the smallest dimension of the residual tumor after initial biopsy would be at least 1 cm [minimal size of single tumor is at least 2 cm in smallest dimension]. It is suggested that core biopsies be submitted separately into individual tissue blocks.

NOTE: Reimbursement guidelines for research biopsies are outlined in [Appendix XI](#).

Forms and Reports:

The following items are to be included with the pathology materials:

- Institutional Diagnostic and Surgical Pathology Report
- ECOG-ACRIN Generic Specimen Submission Form (#2981v3) [if STS is unavailable]
- Sample Tracking System (STS) Shipping Manifest Form
- Immunological study reports, if available

Mail pathology materials to:

ECOG-ACRIN Central Biorepository and Pathology Facility
MD Anderson Cancer Center

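### The local surgical pathology report must travel with the resection specimen to central review and no masking is specified, so local-central agreement on pCR may be overstated

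*Combined protocol and SAP*

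**What the plan says.** **What must be sent.** Section 10.1.1 lists, among the items obligatory with all pathology submissions, a "Copy of the institutional diagnostic and surgical pathology reports". Appendix I repeats it as "Institutional Diagnostic and Surgical Pathology Report".

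**Why it is sent.** Section 7.2 footnote 1 says that tissue "from the surgical resection with the related pathology reports must be submitted for central diagnostic review", and warns that a case may become unevaluable if required materials are missing. The opening of Section 10 likewise requires tissue and related reports: those "from the surgical resection after eight (8) weeks of treatment must be submitted for central diagnostic review".

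**What central review does with it.** Section 11.1 says that the baseline and resection tissue "is required for central diagnostic review to determine patient evaluable for the trial and for central pathologic response assessments". Section 10.1 also names both purposes. Sections 6.1.1 and 6.1.5.1 make the central review retrospective.

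**Routing.** Material goes first to the central biorepository. Section 10.3 then states: "Pathology materials will be distributed to investigators for central pathology review". Its de-identification rule covers specimens released to approved research projects and says nothing about the local result.

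**What the reads are used for.** Section 9.2 bases the primary endpoint on the local read: "A pCR will be defined as the absence of residual viable melanoma in the resected metastasis site as assessed on local pathology review". Objective 2.3.2 is "To compare local review for pathologic response with central pathology review". Section 9.1 lists this comparison among the secondary endpoints, and Section 9.5 plans a concordance analysis by Kendall's Tau, without a target value or power.

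**The concern.** A comparison of two readers measures reliability only if the second reader does not know the first reader's answer. Here the local read already exists when central review takes place, and the document that would normally record it is a compulsory enclosure with the tissue. No step keeps it from the person who scores response.

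What is at stake is how the concordance result can be interpreted. Section 1.4 calls pCR an investigational endpoint in melanoma, and Section 1.7 includes evaluating its role as an endpoint among the trial's purposes. Central review is the only planned check on the local pCR calls. If the central reader has seen those calls, high agreement could mean either that local reads are reliable or that the second reader followed the first. The analysis in Section 9.5 cannot separate the two.

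**Working it through.** **Step 1: document check.** I set side by side every section that deals with central pathology: 1.7, 2.3.2, 6.1.1, 6.1.5.1, 7.2, 9.5, 10 to 10.1.3, 10.3, 11.1 and Appendix I.

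| Question | Answer in the document |
|---|---|
| Must the surgical pathology report accompany the resection tissue? | Yes: 7.2 footnote 1, opening of 10, 10.1.1, Appendix I |
| Is that submission for central review? | Yes: 7.2 footnote 1, opening of 10 |
| Does the same review give the central response category? | Yes: 10.1, 11.1 |
| Is the response reader masked, or the report redacted? | Not stated anywhere |
| Is the report passed from biorepository to reader before scoring? | Not stated (10.3 is silent) |
| Must the report state a pCR, pPR or pNR category? | Not stated |

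The first three rows establish the exposure. The last two limit it to a risk.

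**Step 2: is the primary analysis touched?** The inputs from Section 9.3 are 14 then 39 evaluable patients, stopping at 5 or fewer pCRs and a positive result at 18 or more, with rates of 33% and 57%. The exact two-stage binomial calculation gives type I error 0.0476, power 0.873 and early-stopping probability 0.699 under 33%. These reproduce the stated approximately 0.05, 87% and 70%. Only local reads enter the rule, so masking the central reader changes none of them.

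**Step 3: illustration of size.** The document gives no concordance figure to reproduce, no reader error rate and no rate at which a reader adopts an earlier call. The assumptions are:

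- pCR rate *p* = 0.57 (the Section 9.3 alternative) and 39 patients with both reads
- each reader wrong with probability *e*, independently
- a fraction *d* of would-be disagreements resolved to the local call

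Formulas:

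- Agreement: A(d) = 1 − (1 − d) × 2e(1 − e)
- Probability that a reader calls pCR: m = p(1 − e) + (1 − p)e, the same for both readers and unchanged by *d*
- Chance agreement: C = m² + (1 − m)²
- Kappa = (A − C) / (1 − C). With equal margins in a 2×2 table this equals phi, and hence Kendall's tau-b.

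For e = 0.10: m = 0.57 × 0.90 + 0.43 × 0.10 = 0.556, and C = 0.556² + 0.444² = 0.506. Then:

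- d = 0: A = 1 − 0.18 = 0.820; kappa = (0.820 − 0.506) / 0.494 = 0.64; discordant 39 × 0.18 = 7.0
- d = 0.25: A = 1 − 0.135 = 0.865; kappa = 0.73; discordant 39 × 0.135 = 5.3
- d = 0.50: A = 1 − 0.09 = 0.910; kappa = 0.82; discordant 39 × 0.09 = 3.5

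Varying the error rate:

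| Reader error | Kappa, d = 0 | Kappa, d = 0.25 | Kappa, d = 0.50 |
|---|---|---|---|
| 5% | 0.81 | 0.86 | 0.90 |
| 10% | 0.64 | 0.73 | 0.82 |
| 15% | 0.49 | 0.61 | 0.74 |

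In this model 1 − kappa(d) = (1 − d) × (1 − kappa(0)). Any adoption of the local call therefore moves the result toward agreement, and none leaves it unchanged.

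**The case against.** **The document does not say that the response reader sees the report.** This stands. Reports are sent to the biorepository, and Section 10.3 does not say whether they are forwarded with the tissue. A reader might infer that the central read is not independent and that the comparison is biased. The document supports only that independence is unprotected. Section 1.7 describes central review as customary in this group's melanoma studies. Its working procedure is not part of the document, so masking in practice can be neither shown nor excluded.

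**The content of the report is inferred.** This also stands. No section requires the institutional report to state a response category. The inference is strong, because local pCR is the absence of viable tumor on local pathology, which is what such a report would be expected to record. It remains an inference.

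**The report has proper uses.** Central review also serves evaluability and diagnosis. Section 10.1.2 wants a three-dimensional node measurement in the gross description sent with the specimen, and sites may submit only representative slides per block. Requiring the report is therefore not an error in itself. This does not remove the point, since the gross description and measurements can be passed on without the local microscopic diagnosis.

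**The illustration rests on assumptions.** This is correct. The adoption rate creates the effect. If difficult specimens mislead both readers, masked agreement is already higher and the effect smaller. Patients without surgery have no specimen, so fewer than 39 may have both reads.

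**Conclusion.** The point holds as an unprotected risk. The plan obliges sites to send the local surgical pathology report with the resection tissue for central review, and it specifies no masking for the central response read. Agreement in the Section 9.5 analysis may therefore be overstated. Any such bias would be toward agreement.

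Its size is unknown and is zero if the response reader does not use the report. Under the stated assumptions (57% pCR, independent error of 10%), adopting the local call in a quarter to a half of would-be disagreements raises kappa from 0.64 to between 0.73 and 0.82. At 5% and 15% error the masked values are 0.81 and 0.49, rising to 0.90 and 0.74 at one half.

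A reader might go further and infer that the 18-of-39 verdict is compromised. The document does not support that. The rule counts local pCR calls, central review is retrospective and enters no decision rule, and the design's operating characteristics are as stated. What is weakened is objective 2.3.2 and any use of central concordance as reassurance about the local reads.

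**What to change.** In Section 7.2 footnote 1, Section 10.1.1, Section 10.3 and Appendix I, state for the post-neoadjuvant resection specimen that:

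- sites submit the report to the biorepository as now;
- the biorepository gives the central response reader only the gross description, node measurements and block key;
- the local microscopic or final diagnosis, and any local response category, are withheld until the central response category is recorded and locked;
- the full report may then be released for adjudication.

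The cost is protocol wording and one redaction or routing step per case at a repository that already receives and forwards the material. No new reader, specimen or visit is needed, and because central review is retrospective, no patient decision waits on it. If the reader is already masked in practice, the added text simply documents that. The change is best made before central reading starts, since a reader who has seen the local diagnosis cannot give an independent read of that case afterwards.
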